4 * **Describe the amount of time it will take to complete the entire study:**

Approximately 5 years to complete

5 * **Describe any additional participant requirements:**

None

Sample Size and Data Analysis

If you uploaded a separate research protocol document in the 'Research Protocol' page, cite the applicable section and page numbers from that document in the answer boxes below.

1 * Provide the rationale and sample size calculations for the proposed target population:

We calculated sample size for a Cohen's d effect size equal to 0.31 (at week 12) based on prior studies of Pregabalin for PTSD (Baniasadi et al., 2014) and AUD (Martinotti et al., 2010). We assumed cumulative attrition equal to 25% and correlation among repeated measures equal to 0.55. With a power = 0.80 and alpha-level = .05/2 = .025 (i.e., corrected for two main effect hypotheses), the required sample size is N = 198. The online RMASS (Repeated Measures and Sample Size) calculator based partly on Hedecker (1999) was used to perform the calculation.

2 * Provide the plan for data analysis. Include in the description the types of comparisons that are planned (e.g., comparison of means, comparison of proportions, regressions, analysis of variance, etc.), which is the primary comparison/analysis, and how the analyses proposed will relate to the primary purposes of the study:

Analysis Population: All randomized AUD/PTSD African-American participants who received at least one dose of medication. NOTE: This means that we will NOT test Specific Aim 3 – there were not enough European Americans recruited into the sample to conduct a comparison by race.

A. Describe the sample

Variables/measures we will use to describe the sample are:

- Demographics: age, sex/gender, education, SES (income and employment), collected at screening
- Life events checklist, collected at screening
- PCL, collected at screening
- CAPS, collected at screening
- TLFB30 drinks per week (DPW), drinks per drinking day (DPDD), heavy drinking days (HDD); collected at screening
- OCDS, collected at baseline
- CIWA, collected at baseline
- AUD severity defined as a symptom count from the SCID
- Smoking status defined as smoking >= 10 cigarettes in past 90 days from the "Other Drug Use" form
- Vital signs: BMI calculated from height and weight, collected at screen

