Data collection took place at the University of Maryland School of Medicine in Baltimore, MD. Data collection began in July 2017 and ran until June 2019 when the research center where the study was running shut down. The study resumed at a new research center in July 2019 and ran until research was shut down due to the COVID 19 pandemic in March 2020. Data collection resumed in October 2020 and, with the exception of a one-month COVID-related shutdown in January 2021, ran until the data collection window closed in December 2021.

Because of these interruptions in data collection, we modified data analysis plans and performed a power analysis based on the new analytic approach. We calculated sample size for a Cohen's d effect size equal to 0.31 (at week 12) based on prior studies of pregabalin. We assumed cumulative attrition equal to 25% and correlation among repeated measures equal to 0.55. With power=0.80 and alpha-level=.05/2=.025 (2 main effect hypotheses), the required sample size was N=198 randomized. The online RMASS (Repeated Measures and Sample Size) calculator based partly on Hedecker (1999) was used to perform the calculation.

This study randomized n=54 Black/AA participants. The final analysis sample size for this study was N = 44 with n1=26 randomized to receive Pregabalin and n2=18 randomized to receive placebo. We re-calculated power for specific aims 1 and 2 based on the modified primary analysis model, achieved sample sizes, observed attrition rates (cumulative attrition at time point 12 equaled 40%), and average correlation among repeated measures (equal to 0.53 for HDD). We used the RMASS (Repeated Measures and Sample Size) online calculator (<http://www.rmass.org>) which incorporates methods developed in several articles for longitudinal designs. Under the above specifications, the detectable Cohen's d type effect size for HDD equaled 0.67 with two-sided alpha set=0.05 and power=0.80. Under the same specifications for specific aim 2 for cluster B and E subscales of the PCL-5, except for slight changes to the correlation, detectable effect sizes equaled 0.68 and 0.63.

Analysis Population: All randomized AUD/PTSD African-American participants who received at least one dose of medication. **NOTE:** This means that we will NOT test Specific Aim 3 – there were not enough European Americans recruited into the sample to conduct a comparison by race.

A. Describe the sample

Variables/measures we will use to describe the sample are:

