- Demographics: age, sex/gender, education, SES (income and employment), collected at screening
- Life events checklist, collected at screening
- PCL, collected at screening
- CAPS, collected at screening
- TLFB30 drinks per week (DPW), drinks per drinking day (DPDD), heavy drinking days (HDD); collected at screening
- OCDS, collected at baseline
- CIWA, collected at baseline
- AUD severity defined as a symptom count from the SCID
- Smoking status defined as smoking >= 10 cigarettes in past 90 days from the "Other Drug Use" form
- Vital signs: BMI calculated from height and weight, collected at screen

B. Specific Aim 1 (SA1): To test the hypothesis that African American AUD/PTSD participants treated with pregabalin will demonstrate a greater reduction in heavy drinking days than African American placebo treated participants.

Primary outcome: HDD during the past 7 days assessed weekly during treatment with the TLFB. **NOTE:** We will adjust for drinking last 30 days at screening.

Secondary outcomes:

- DPW and DPDD during the past 7 days assessed weekly during treatment with the TLFB.
- Number of days abstinent (NDA) during the past 7 days assessed weekly during treatment with the TLFB. **NOTE:** We will adjust for drinking last 30 days at screening.
- %dCDT measured via blood samples collected at screening, midpoint (Visit 6), and end-of-study (Visit 12).
- GGTP measured via blood samples collected at screening, midpoint (Visit 6), and end-of-study (Visit 12).

SA1 Analysis: For HDD and secondary TLFB outcomes, a repeated measures mixed effects model will be used to compare change over the twelve weekly assessments between the two treatment conditions. The model will be a generalized linear or linear model depending on the distribution of the outcome. A quadratic term for time will be specified to capture non-linear change. To reduce residual error and maximize power, we will adjust for a pre-baseline assessment of the outcome. Overall, the regression model will be:

$$\text{Outcome} = \text{pre-baseline Outcome} + \text{txgroup} + \text{week} + \text{week2} + \text{weekXtxgroup} + \text{week2Xtxgroup}$$

The analysis model for %dCDT of and GGTP will assess the time-averaged (over visits 6 and 12) difference between treatment groups adjusting for baseline. The model will account for within-individual correlations with a random effect for participant.

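### The SAP plans Aims 1 and 2 at alpha 0.025 but recalculates their detectable effects at 0.05, and the protocol still reports only 80% power with 198

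*SAP*

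**What the plan says.** The planning calculation in SAP Item 3 starts from the planned effect: "We calculated sample size for a Cohen's d effect size equal to 0.31 (at week 12) based on prior studies of pregabalin". It continues: "We assumed cumulative attrition equal to 25% and correlation among repeated measures equal to 0.55". At power 0.80, and with alpha halved from 0.05 to 0.025 for two main-effect hypotheses, it concludes that "the required sample size was N=198 randomized".

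The next paragraph reports what was achieved. 54 Black/AA participants were randomised, and "The final analysis sample size for this study was N = 44", split 26 pregabalin and 18 placebo. Cumulative attrition was 40% at time point 12, and the average correlation was 0.53 for heavy drinking days (HDD). Power for Aims 1 and 2 was recalculated "based on the modified primary analysis model". At two-sided alpha 0.05 and power 0.80, the detectable effects are 0.67 for HDD and 0.68 and 0.63 for PCL-5 clusters B and E.

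The model under SA1 Analysis has twelve weekly assessments and adjusts for the pre-baseline outcome. On time it says: "A quadratic term for time will be specified to capture non-linear change". Week and week squared both interact with treatment. No single term or contrast is named as the primary test, and the SA1 and SA2 analysis text gives no significance level.

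The protocol (Sample Size and Data Analysis, question 1) repeats the planning inputs and says that "the required sample size is N = 198". Question 2 of the same section already records that too few European Americans were recruited to test Aim 3. The section mentions neither the 44 analysed nor the detectable effects.

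**The concern.** Both calculations serve the same two aims, but one carries the correction for two hypotheses and the other does not. A reader who sets 0.67 beside 0.31 is therefore comparing figures on different error rates, and the achieved sensitivity looks better than it is under the plan's own correction. A reader of the protocol alone sees 80% power and 198 participants, in text written when it was already known that recruitment had fallen short.

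These figures are the modified plan's only statement of sensitivity. If they are taken at face value, a null result in 44 people could be read as evidence against the planned effect.

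**Working it through.** **1. Can the stated figures be reproduced?** I used the two-group repeated-measures formula N = 4(z_α + z_β)²V/d². V is the variance factor of the chosen contrast under generalised least squares. Assumptions: equal correlation between visits, dropout rising linearly to the stated cumulative value, and a normal approximation. For unequal arms, the detectable d is (z_α + z_β)√[V(1/26 + 1/18)]. The inputs are those of SAP Item 3: ρ=0.55 and 25% attrition for planning, ρ=0.53 and 40% attrition as observed.

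| Set-up | N at d=0.31 | Detectable d, 26 v 18, two-sided 0.05 |
|---|---|---|
| Constant difference, 12 assessments | 197 at two-sided 0.05 | 0.66 |
| Linear slope, 11 assessments | 198.1 at two-sided 0.025 | 0.668 |
| Quadratic model, first-to-last change, 11 assessments | 199.0 at two-sided 0.025 | 0.674 |

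Example, row 2: V=0.5007, so N = 4 × 3.083² × 0.5007 / 0.31² = 198.1. The stated pair of 198 and 0.67 therefore fits more than one set-up. Two of them use exactly the alphas that the SAP states.

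**2. Put the detectable effects on the planned alpha.** This step needs no contrast. A detectable effect is (z_α + z_β) times the standard error.

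- Two-sided 0.05: 1.960 + 0.842 = 2.802.
- Two-sided 0.025: 2.241 + 0.842 = 3.083.
- Ratio: 3.083 / 2.802 = 1.100.

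**3. Power of the 44 at d=0.31.** The implied standard error is the stated effect divided by 2.802. Power is Φ(0.31/SE − z_α). For HDD, SE = 0.67/2.802 = 0.239 and 0.31/0.239 = 1.296. Power is Φ(1.296 − 1.960) = 25% at 0.05 and Φ(1.296 − 2.241) = 17% at 0.025.

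| Outcome | Stated d (0.05) | d at 0.025 | Power at 0.31, alpha 0.05 | Power at 0.31, alpha 0.025 |
|---|---|---|---|---|
| HDD | 0.67 | 0.74 | 25% | 17% |
| PCL cluster B | 0.68 | 0.75 | 25% | 17% |
| PCL cluster E | 0.63 | 0.69 | 28% | 19% |

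**4. Does the contrast change the picture?** These are computed directly from the model, with twelve assessments and before any gain from baseline adjustment. The last three rows are contrasts of the quadratic model. The 2-df row assumes that the difference grows linearly from week 1 to 0.31 at week 12.

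| Contrast | 198, alpha 0.025 | 44, alpha 0.025 | 44, alpha 0.05 |
|---|---|---|---|
| Constant difference | 71% | 18% | 26% |
| First-to-last change | 83% | 18% | 27% |
| 2-df interaction test | 74% | 14% | 21% |
| Week-12 difference | 53% | 11% | 17% |

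A linear slope without quadratic terms gives 19% and 27% for the 44. Across contrasts the 44 have about 11–19% power at 0.025 and 17–27% at 0.05.

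**The case against.** **The SAP is open about the shortfall.** It gives the 44, the 40% attrition, the alpha used and detectable effects about twice the planned 0.31. That is true, and a careful reader can do the rescaling. The change of alpha is still unexplained, and none of this appears in the protocol.

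**The sidedness of 0.025 is not stated.** One-sided 0.025 and two-sided 0.05 share the critical value 1.960. On a one-sided reading the rescaling in step 2 disappears and the power of the 44 is about 25%. This cannot be excluded. However, the SAP attributes the halving to two hypotheses rather than to one-sided testing, and it calls its recalculation two-sided.

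**Baseline adjustment could raise power.** The documents do not quantify the gain. Suppose that 0.55 and 0.53 are unadjusted correlations, that d is on the unadjusted SD scale and that the baseline correlates equally with follow-up. Constant-difference power at 0.025 would then be about 96% for 198 and 33% for 44. Even so, the 44 remain far below 80%.

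**A stronger reading is tempting.** A reader might infer that 198 and 0.67 cannot come from the stated model, and so that 80% power with 198 is overstated. The documents do not support this. With twelve assessments, the first-to-last change contrast needs 185 at two-sided 0.025, so 198 gives 83%. With eleven, which is plausible because Visit 1 is the baseline visit with the starting dose, both figures reproduce at the SAP's own alphas. Equally, 198 gives only 53% for a week-12 difference. The calculator's inputs are not given, so no arithmetic error in 198 is established.

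**Conclusion.** The concern holds in a limited form. SAP Item 3 uses 0.025 to plan Aims 1 and 2 and 0.05 to report what the achieved sample can detect, without a reason. Against the plan's own correction the three detectable effects are about 10% too favourable: 0.74, 0.75 and 0.69 instead of 0.67, 0.68 and 0.63. Taking the SAP's values at face value, the 44 have 17–19% power at d=0.31 with alpha 0.025 and 25–28% with 0.05. The protocol gives 80% with 198 and nothing on the achieved sample.

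The rescaling assumes a normal approximation and a two-sided 0.025. The contrast-specific ranges also assume equal correlation, monotone dropout and no gain from baseline adjustment. The finding that the 44 are well short of 80% at d=0.31 survives every variation tried. Whether 198 would have given 80% remains open.

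**What to change.** In SAP Item 3, restate the three detectable effects at alpha 0.025, with sidedness, for the contrast that will be tested, and give the power of the 44 at d=0.31. If 0.05 is intended for the tests, say so and justify dropping the correction.

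In the protocol's sample-size answer, label 80% with 198 as the planning figure that was not achieved, and add the 44 analysed with their power at d=0.31. In both documents, state that a non-significant result does not rule out d=0.31.

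The cost is a few sentences and figures that look less favourable. No extra patients or data are needed.

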C. Specific Aim 2 (SA2): To test the hypothesis that African American AUD/PTSD participants treated with pregabalin will demonstrate a greater reduction in PTSD cluster B or E symptoms (or both) than African American placebo-treated participants.

Primary outcomes:

- PCL cluster B symptom severity scores, assessed weekly during treatment.
- PCL cluster E symptom severity scores, assessed weekly during treatment.
- NOTE: We will adjust for PCL score collected at screening.

Secondary outcomes:

- PCL total symptom score, assessed weekly during treatment. NOTE: We will adjust for PCL score collected at screening.
- CAPS cluster B and E symptom severity scores, assessed at weeks 4, 8, and 12 during treatment. NOTE: We will adjust for CAPS score collected at screening.

SA2 Analysis: The analysis of the primary outcomes will use the same regression model described for drinking outcomes in SA1. Analysis of the CAPS scores will be a repeated measures mixed effects model to test the difference in the mean across weeks 4, 8, and 12 adjusting for the pre-baseline score.

D. Specific Aim 4 (SA4): To test the hypothesis that the treatment responses to pregabalin in African American AUD/PTSD participants specified in SA1 and SA2 are moderated by genetic variations within SLC6A1 gene.

Analysis: This analysis will examine whether there is a difference of treatment effect between two SLC6A1 gene variant groups, i.e., the non-insertion/insertion or insertion/insertion variant group (NI/I or I/I) versus the non-insertion/non-insertion (NI/NI) variant. A binary indicator will be constructed to indicate the NI/I or I/I versus NI/NI variant. The analysis will be conducted by adding the main effect and interaction terms of this binary indicator to the above regression model to test whether there is a difference in treatment effect by SLC6A1 gene group on the primary outcomes specified in SA1 and SA2.

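### The SAP sizes the modified trial at .05/2 = .025 but reports its detectable effects at uncorrected two-sided 0.05, and it does not divide Aim 2's .025 between PCL clusters B and E

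*SAP*

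**What the plan says.** **Sizing.** SAP Item 3 (modified plan) states: "With power=0.80 and alpha-level=.05/2=.025 (2 main effect hypotheses), the required sample size was N=198 randomized". The Protocol, Sample Size and Data Analysis, item 1, gives the same level and its reason: "alpha-level = .05/2 = .025 (i.e., corrected for two main effect hypotheses". The two hypotheses match Specific Aims 1 and 2. Neither document says whether .025 is one- or two-sided.

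**Re-calculation.** The next paragraph of SAP Item 3 uses the achieved sample (26 pregabalin, 18 placebo), 40% cumulative attrition and a correlation of 0.53. The detectable Cohen's d "type effect size for HDD equaled 0.67 with two-sided alpha set=0.05 and power=0.80". Aim 2 follows: "Under the same specifications for specific aim 2 for cluster B and E subscales of the PCL-5", apart from slight changes in correlation, "detectable effect sizes equaled 0.68 and 0.63". So 0.05 applies to all three figures.

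**Primary outcomes.** Aim 1 has one: "HDD during the past 7 days assessed weekly during treatment with the TLFB". Aim 2 has two: "PCL cluster B symptom severity scores, assessed weekly during treatment" and "PCL cluster E symptom severity scores, assessed weekly during treatment". The Aim 2 hypothesis is met by an advantage on cluster B, cluster E or both.

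**Testing rule.** The aim-by-aim analysis sections (SAP Item 3, B to D; Protocol, Sample Size and Data Analysis, item 2) give the models. They state no significance level, hierarchy or division of alpha.

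**The concern.** Two things do not fit together.

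First, the correction used to justify N=198 is missing one paragraph later, without explanation. The figures 0.67, 0.68 and 0.63 are the plan's own statement of what 44 participants can show. A reader who sees the corrected sizing just above will take them as being on the same footing, and they are not.

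Second, the correction counts two hypotheses, but three primary outcomes are tested and either of two can carry Aim 2. If each cluster is tested at the full .025, Aim 2 uses more than its share. If they share .025, it does not. The text does not say which. If the smaller of the two cluster p-values lies between .0125 and .025, Aim 2 is met under one reading and not under Holm within .025. The SAP carries an IRB approval date of 10/28/2022 and already reports achieved numbers, while data collection closed in December 2021. A rule still open at that stage could be settled after the results are seen.

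**Working it through.** **1. Which alpha lies behind each stated figure?**
Inputs for N=198 (SAP Item 3): d = 0.31 at week 12, correlation 0.55, attrition 25%, power 0.80, 12 weekly assessments, 1:1 allocation. The calculator settings are not given. I assumed a linear-trend contrast, equal correlation between visits, and attrition applied as 1/(1 − 0.25).
- N = 4(z_α + z_β)² × V / d² / 0.75. With week coefficients centred at zero, V = (1 − 0.55) × 143/169 = 0.381.
- Two-sided .025: z_α + z_β = 2.241 + 0.842 = 3.083, so N = 4 × 9.505 × 0.381 / 0.0961 / 0.75 ≈ 201.
- Two-sided .05: z_α + z_β = 1.960 + 0.842 = 2.802, so N ≈ 166.

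The stated 198 is close to the .025 result and far from the .05 result.

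For the HDD effect with 26 and 18 participants, correlation 0.53 and 40% attrition:
- d = (z_α + z_β) × √[(1/26 + 1/18) × 0.47 × 143/169 / 0.60] = 0.70 at .05 and 0.77 at .025.
- With gradual dropout the same contrast gives 0.65 at .05 and 0.71 at .025.

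The stated 0.67 lies inside the .05 range (0.65 to 0.70) and below the .025 range (0.71 to 0.77). This agrees with the text: two levels were used. Neither figure is matched exactly.

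**2. The stated effects at the plan's own .025**
For a test with one degree of freedom, two-sided:
- Power at the stated effects = Φ(2.802 − 2.241) = Φ(0.560) = 0.712.
- Ratio of detectable effects = 3.083 / 2.802 = 1.100.
- HDD: 0.67 × 1.100 = 0.74. Cluster B: 0.68 × 1.100 = 0.75. Cluster E: 0.63 × 1.100 = 0.69.

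At .0125, the first Holm step if B and E share .025:
- z_α = 2.498 and the ratio is 3.339 / 2.802 = 1.192.
- Cluster B: 0.68 × 1.192 = 0.81. Cluster E: 0.63 × 1.192 = 0.75.
- Single-cluster power at the stated effects = Φ(2.802 − 2.498) = 0.619.

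**3. Chance of a false primary claim**
The documents do not give the correlations of the test statistics. I assumed 0.5 to 0.8 between B and E, and 0 to 0.3 between HDD and either cluster. Each outcome has one two-sided normal test. Aim 2 figures come from the bivariate normal; three-outcome figures come from 4,000,000 simulated draws per setting.

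| Rule | Scope | Chance of at least one false claim |
|---|---|---|
| .025 for each cluster | Aim 2 | 4.65% at correlation 0.5, 4.02% at 0.8 (independent: 1 − 0.975² = 4.94%) |
| .025 for each outcome | All three as one family | 6.3 to 7.0% (independent: 1 − 0.975³ = 7.3%) |
| HDD .025, B and E .0125 each | All three as one family | 4.4 to 4.8% (upper bound .025 + .0125 + .0125 = 5%) |
| .05 for each cluster | Aim 2 | 7.8 to 9.1% (independent: 1 − 0.95² = 9.75%) |

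The last row is for reference only, because the plan does not state that rule.

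**The case against.** The strongest reply is that the plan does have an alpha. The Protocol says in words that .025 is a correction for two hypotheses, the SAP repeats it, and the two hypotheses are Aims 1 and 2. On that reading only the division inside Aim 2 is missing. This stands, and the point is framed accordingly.

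A reader might go further and infer that the modified plan adopts no alpha, or that all three outcomes will be judged at 0.05, with a 12.1 to 13.6% chance of some false primary claim. The documents do not support that. In SAP Item 3 the 0.05 is a setting in a re-calculation of detectable effects, and nothing says that results will be judged at it. The two-sided .05 stated as a testing level elsewhere in the SAP belongs to the original single composite outcome, which the modified plan replaces.

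Three further replies have weight:
- **The family is a judgement.** If Aims 1 and 2 are separate families, the 6.3 to 7.0% figure does not apply. If Aim 2 is also allowed a full 5%, then .025 on each cluster stays within it. But the plan gave each aim .025, and against that share 4.0 to 4.7% is an excess.
- **The power change alters no decision.** Both 0.67 and 0.74 are more than twice the planned 0.31. This is true; the correction makes the statement accurate and does not rescue the trial.
- **The first-step figures overstate the loss for Aim 2.** Either cluster is enough. If both effects are real at the stated sizes, the chance that at least one passes .0125 is about 72 to 78% (correlation 0.8 to 0.5), above the 62% for a single cluster.

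**Conclusion.** The point holds in two limited parts.

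1. The detectable effects of 0.67, 0.68 and 0.63 omit the correction that the plan applied to its own sample size. With .025 taken as two-sided, they carry about 71% power, and the 80%-power effects are about 0.74, 0.75 and 0.69. These are single-degree-of-freedom rescalings and are illustrative, since each primary model has three treatment terms and the plan does not single one out.

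2. Aim 2 is counted as one hypothesis but can be met through either of two primary outcomes, and its .025 is not divided. Testing B and E at .025 each gives about 4.0 to 4.7% against a 2.5% share, and about 6.3 to 7.0% over all three outcomes if they are one family. Both ranges rest on the assumed correlations. If B and E share .025, the total stays within 5%.

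The mismatch of levels and the missing division are certain from the text; the percentages are conditional. The excess at the stated .025 is modest, but the missing rule decides whether Aim 2 is met in borderline cases, so it should be fixed.

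**What to change.** 1. Carry the stated .025 per aim into the analysis sections of both documents (SAP Item 3, Aims 1 and 2; Protocol, Sample Size and Data Analysis, item 2). Suggested wording: HDD is tested at two-sided .025. PCL clusters B and E are tested by Holm within a total two-sided .025, the smaller p-value against .0125 and, if that is significant, the larger against .025. Aim 2 is met if either is significant. This holds the total at 5%.

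2. Recompute the detectable effects at those levels (about 0.74 for HDD, and about 0.81 and 0.75 for B and E at the first Holm step), or keep 0.67, 0.68 and 0.63 and label them as uncorrected for multiplicity.

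3. State that the rule was added after data collection closed in December 2021, unless blinding at that time is documented.

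The cost is a few sentences and one re-run of the calculator, with no patients or new data. The downsides are that the stated detectable effects become about 10% (at .025) to 19% (at .0125) less favourable, and that the rule counts as post hoc unless blinding can be shown.
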